13.3 Sample Size and Power Considerations

Given that the purpose of this Phase 2a trial is to determine whether the drug is efficacious and therefore whether to proceed with further development, there is only 1 outcome of interest: superiority of 1 or more experimental arms to the control. In this scenario, a one-sided testing framework is appropriate.

Moreover, given the need for the trial to be small (one or more Phase 3 trials will be required to confirm the efficacy), standard type I error rate control at the 2.5% level is not strictly necessary. For decisions concerning the future of the project, the sponsor will consider a more relaxed approach to false positive rate, allowing a 5% type I error for the one-sided test of the null hypothesis (ie, the primary outcome is no different between each treatment group and control) rather than the usual 2.5% required for a pivotal trial. The use of this higher type I error and of a low type II error of 15% give to the trial a high statistical power to detect the clinically meaningful effects while maintaining an acceptable and feasible size. Finally, because this trial is

a multiple-experimental arm randomized trial with a control, sample size is increased in order to maintain an overall type I error rate as close as possible to the nominal value of 5%. Assuming the following:

- A 6% Clinical Remission rate for the placebo, which after allowing for a 15% dropout rate being interpreted as treatment failure, equates to a 5.1% Clinical Remission rate.
- A 26% Clinical Remission rate for the highest dose of GED-0507-34-Levo (20% more than placebo group), which after allowing for a 15% dropout rate being interpreted as treatment failure, equates to a 22.1% Clinical Remission rate.
- A type I (α) error of 0.05.
- A power of 85%, type II (β) error = 0.15, to detect, if it exists, the above stated difference between GED-0507-34-Levo and placebo.
- A one-tailed test for proportions.
- A drop-out rate of 15%.

Fifty five (55) subjects per group are needed.

However, in order to take into account the multiplicity of the tests and the need of maintaining the experiment-wise error at the nominal alpha level, the number of subjects per group is increased to 69, for a total of 207 subjects. With this number of subjects, the alpha level actually considered is 2.5%, as the Bonferroni-Holm method will require for the significance testing of the lower p-value.

Table 2 shows how the statistical power would change if the Clinical Remission rate in the placebo group was different from the estimated 6% (maintaining a 20% greater effect in the treatment group before adjustment for dropouts).

Table 2 Change in Statistical Power Based on Clinical Remission Rate

	# of Estimated Subjects per Group Who Will Complete Study ^a	Clinical Remission Rate			
# of Subjects per Group		Placebo Group	Treatment Group	Type I Error	Statistical Power
69	59	4%	24%	2.5%	89%
69	59	5%	25%	2.5%	87%
69	59	6%	26%	2.5%	85%
69	59	7%	27%	2.5%	83%
69	59	8%	28%	2.5%	81%
69	59	9%	29%	2.5%	80%
69	59	10%	30%	2.5%	78%

a. assuming a drop-out rate of 15%

Computations for sample size and power estimation are performed using the formula of Chow (Chow et al., 2007).

13.4 Statistical Methods

The primary efficacy variable is the proportion of subjects who are in Clinical Remission at Week 8, as defined by an MMS of ≤ 2 , with individual sub-scores (SF and Endoscopy) ≤ 1 , and RBS = 0.

GED-0507-34-Levo treatment arms will be compared with placebo using the chi-squared test and using the Bonferroni-Holm method to control the false positive error rate. Corresponding confidence intervals for the risk ratios of GED-0507-34-Levo against placebo will be presented. Subjects who withdraw will be assumed not to be in remission at Week 8. The last-observation-carried-forward (LOCF) method will be used to impute MMS in the case of missing values in subjects completing the study. The above primary analysis does not adjust for the effects of center under the assumption that there will be many centers who do not recruit at least 1 subject on every treatment. Should this assumption not appear to be the case, the primary analysis methodology will be updated in the SAP prior to breaking the blind for the study.

The primary analysis of the primary efficacy variable will be on the mITT population and will be the comparison of each of the GED-0507-34-Levo doses against placebo as described above.

Additional supportive analysis of the primary efficacy variable will be performed on the ITT and PP populations. A further exploratory log-binomial regression analysis will be performed to investigate the association of prognostic factors with proportion of subjects in Clinical Remission at Week 8.

Summary statistics will be presented for efficacy variables and their changes from baseline at each time point on the mITT, ITT, and PP populations.

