8 OVERALL STUDY DESIGN

8.1 Study Design

This is a Phase 2, multicenter, randomized, double-blind, placebo-controlled, parallel-group study to evaluate the efficacy and safety of 2 doses of GED-0507-34-Levo in subjects with active, mild-to-moderate UC (defined as an MMS of ≥ 4 to ≤ 8 , with a Stool Frequency subscore ≥ 1 , an RBS = 1 or 2, and an endoscopic sub-score ≥ 1 and ≤ 3).

Approximately 207 subjects (69 subjects per arm) will be randomized in a 1:1:1 ratio using an Interactive Web Response System (IWRS) to receive oral GED-0507-34-Levo (80 mg BID) or 160 mg BID) or identically appearing placebo BID for up to 8 weeks. Treatment will be assigned via IWRS.

The study will consist of 3 parts:

- In Part 1, 24 subjects will be randomized with 8 subjects per treatment group. The Safety evaluation (clinical, hematological, and biochemistry) on these 24 subjects will be assessed by an Independent Safety Committee.
- After the 24th subject is enrolled in Part 1, then Part 2 will start in which new subjects will be randomized only in the 80 mg BID and placebo groups in a 1:1 ratio.
- Once the 24 subjects in Part 1 have completed 8 weeks of treatment and the Safety evaluation has been completed with no safety concerns, then Part 3 will continue to enroll subjects randomized into all 3 treatment groups. An unequal randomization will be used in Part 3 of the study in order to ensure approximately equal numbers of subjects randomized into each of the 3 treatment groups across the 3 study parts.

The study will consist of 3 phases:

- Screening Phase up to 4 weeks
- Double-blind Placebo-controlled Phase Week 0 to Week 8
- Follow-up Phase Week 9

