8.1.1 Safety/PK Sub-studies

Safety will be assessed on the first 24 randomized subjects (8 in 160 mg/day, 8 in 320 mg/day, and 8 in Placebo group) by an Independent Safety Committee before more subjects in the high dose group are enrolled in the study.

After enrollment of subject number 24, and until the Independent Safety Evaluation is complete, enrollment will continue and subjects will be randomized in the placebo and 80 mg BID (160 mg/day) dose groups.

Upon completion of the Independent Safety Evaluation and provided a positive safety outcome is obtained, enrollment of subjects in the 3 dose groups will be performed until end of study.

A PK sub-study will be conducted at selected sites. The target for the PK sub-study is to achieve participation of approximately 50% of the randomized subjects

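### The 160 mg versus placebo test pools three enrolment Parts with different allocation, so it is exposed to any change in remission rate between Parts 2 and 3; a Part-stratified analysis should be prespecified beside it

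*Combined protocol and SAP*

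**What the plan says.** **Allocation.** Section 8.1 puts 24 subjects into Part 1, 8 per arm. In Part 2, "new subjects will be randomized only in the 80 mg BID and placebo groups in a 1:1 ratio". Section 8.1.1 leaves Part 2 open-ended: "until the Independent Safety Evaluation is complete, enrollment will continue and subjects will be randomized in the placebo and 80 mg BID". Part 3 starts "Once the 24 subjects in Part 1 have completed 8 weeks of treatment and the Safety evaluation has been completed with no safety concerns". Arm totals are to be evened out at that stage: "An unequal randomization will be used in Part 3 of the study in order to ensure approximately equal numbers of subjects randomized into each". The Part 3 ratio and the size of Part 2 are not given.

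**Ratio wording.** Section 8.1 also states "Approximately 207 subjects (69 subjects per arm) will be randomized in a 1:1:1 ratio". Section 11.3 gives 1:1:1 assignment at baseline without mentioning the Parts.

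**Analysis.** Section 13.4: "GED-0507-34-Levo treatment arms will be compared with placebo using the chi-squared test and using the Bonferroni-Holm method". It explains only why center is left out, and foresees a change of method only on that account: "Should this assumption not appear to be the case, the primary analysis methodology will be updated in the SAP prior to breaking the blind". The one regression is exploratory and names no factors: "A further exploratory log-binomial regression analysis will be performed to investigate the association of prognostic factors". Section 13.6 applies similar methods to the secondary endpoints. Section 13.1 leaves the comprehensive plan to a separate SAP, which is not among the documents.

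**The concern.** Over the whole trial, 160 mg and placebo are not enrolled at the same times. Placebo collects subjects in all three Parts, whereas 160 mg has none in Part 2 and proportionally more in Part 3. A pooled 2×2 comparison treats the two groups as if they were concurrent. If the underlying remission rate moves between Parts 2 and 3, part of that movement is read as a 160 mg effect, in either direction.

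Section 13.3 powers the trial on the highest dose and enlarges the groups from 55 to 69 to hold the overall error near 5%. The exposed comparison is therefore the one that drives the size of the trial and bears on the decision about further development. Bonferroni-Holm deals with having two doses; it does nothing about a shift in rate over time.

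**Working it through.** **1. The plan's own figures.** Inputs from Section 13.3: 5.1% versus 22.1% after counting 15% dropouts as failures, 85% power, one-sided test. With n = (z_α + z_β)² [p₁(1−p₁) + p₂(1−p₂)] / (p₂−p₁)²:
- α = 0.05: (1.645 + 1.036)² × (0.0484 + 0.1722) / 0.17² = 54.9, so 55.
- α = 0.025: (1.960 + 1.036)² × 0.2206 / 0.0289 = 68.5, so 69.

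Both match, as do all seven rows of Table 2. The sample size arithmetic is not in question.

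**2. Cells implied by Section 8.1 with 69 per arm.** Let m = N2/2 be the Part 2 placebo count.

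| | Placebo | 80 mg | 160 mg |
|---|---|---|---|
| Part 1 | 8 | 8 | 8 |
| Part 2 | m | m | 0 |
| Part 3 | 61 − m | 61 − m | 61 |

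At N2 = 36, for example, Part 3 must run 43:43:61.

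**3. Bias with no drug effect** (ignoring mITT exclusions). With rates r₁, r₂, r₃ by Part:
- 160 mg mean = (8r₁ + 61r₃)/69
- placebo mean = (8r₁ + m r₂ + (61−m) r₃)/69
- difference = (m/69)(r₃ − r₂)

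The Part 1 rate cancels. For 80 mg the cells equal those of placebo, so the difference is zero.

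**4. Assumptions needed for size.** N2 and drift are not in the documents.
- *N2.* At steady enrolment N2 = 207 × Part 2 weeks / total enrolment weeks. Part 2 lasts at least 8 weeks. Taking 8 to 12 weeks, N2 is about 16–24 for 104 weeks of enrolment, 32–48 for 52 and 64–96 for 26. Slower early accrual shrinks it.
- *Drift.* A rise from 5.1% to 10%, either as a step at the start of Part 3 (worst case) or linear over the 207 enrolments. In the linear case the Part 2 and Part 3 midpoints lie (183/2) enrolments apart, so the bias is 91.5/207 = 44% of the step bias at any N2.

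**5. Pooled test, neither dose active.** Exact enumeration of arm totals; 160 mg tested at one-sided 0.025; family-wise means either dose rejected. At a constant 5.1%, 160 mg error is 2.4% and family-wise error 4.1% at every N2. With the rise to 10%:

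| N2 | Step bias (points) | 160 mg error, step | Family-wise, step | 160 mg error, linear | Family-wise, linear |
|---|---|---|---|---|---|
| 24 | 12/69 × 4.9 = 0.85 | 3.8% | 5.5% | 3.1% | 5.0% |
| 36 | 18/69 × 4.9 = 1.28 | 4.6% | 6.2% | 3.4% | 5.3% |
| 60 | 30/69 × 4.9 = 2.13 | 6.6% | 8.1% | 4.1% | 5.8% |
| 80 | 40/69 × 4.9 = 2.84 | 8.9% | 10.2% | 4.7% | 6.4% |

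Simulation agrees within 0.2 points (6.7% and 9.1% for the last two 160 mg step values). The 80 mg error stays at 2.4–2.6%. A linear rise to only 7% keeps family-wise error below 5% at each of these N2. A fall reverses the sign: from 10% to 5.1% as a step at N2 = 80, 2.84 points are taken off a true effect.

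**6. Pooled test, 80 mg adds 17 points.** Once 80 mg is rejected, Holm tests 160 mg at 0.05, and this must be counted. Simulated 160 mg error at N2 = 36/60/80 is 8.4/11.6/15.2% (step) and 6.8/7.8/8.7% (linear), against 5.9–6.0% with no drift. That no-drift excess over 5% is not due to the Parts: a single pooled test at one-sided 0.05 already has about 6.0% error at this low rate.

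**7. What stratifying by Part does.** A Cochran-Mantel-Haenszel test by Part takes nothing from Part 2, which has no 160 mg subjects, so it uses only concurrently randomised placebo. Its null error stayed at or below 2.5% in every drift scenario run (largest 2.46%). A three-arm logistic score test with treatment and Part gave 2.3–2.5% under the step with 80 mg inert. Power for 160 mg with no drift (pooled test, 0.025 step: 86%):

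| N2 | Logistic, 0.025, 80 mg inert | CMH, 0.025 | Logistic under Holm, 80 mg equally effective |
|---|---|---|---|
| 24 | about 83% | 81% | about 90% |
| 36 | about 81% | 79% | about 89% |
| 60 | about 76% | 69% | about 87% |
| 80 | about 67% | 55% | about 84% |

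**The case against.** The strongest reply is that the harm is wholly conditional. Nothing in the documents suggests drift, and with a constant rate the pooled test does what was planned. The design keeps the same eligibility and 8-week endpoint in all Parts, and endoscopy is read centrally and blinded (Section 9.7.2). Section 13.3 deliberately relaxes error control, aims only to stay near 5% overall and expects Phase 3 confirmation. By that standard gradual drift does little at small N2, and the 8–10% family-wise values need an abrupt change exactly at the Part 3 boundary together with N2 of 60 to 80. Adjustment costs power for certain, and the separate SAP may already contain a Part term.

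Most of this stands, and it limits what can be claimed. It does not remove the point. Stool frequency and bleeding come from diaries and are not protected by central reading. About 207 subjects at about 85 sites is 2.4 per site, so the site mix can differ between Parts; that is a possible route to drift, not evidence of it. N2 has no cap. Section 13.4 names the primary test and foresees revising it only because of center.

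Three stronger readings are tempting, and the documents do not support them:
- *The planned test has inflated error.* It does only if the rate changes, and no change is documented.
- *The primary test must be replaced.* That exchanges a certain power loss for protection against unproven drift.
- *The SAP omits Part.* It was not available, so this cannot be asserted.

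The 1:1:1 statement in Section 8.1 can also be read as the overall target, since it stands beside 69 per arm and the three Parts follow. Section 11.3 lacks that context.

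**Conclusion.** The point holds as a structural exposure of conditional size. The allocation scheme and the unstratified test together make the 160 mg comparison depend on any difference in remission rate between Parts 2 and 3, by the formula in step 3. The 80 mg comparison is unaffected provided 80 mg and placebo keep equal allocation in Part 3.

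The size is negligible with a stable rate, small when Part 2 is short or drift is gradual and modest, and material only for a large Part 2 with a marked or abrupt change. All drift figures rest on assumed N2 and assumed rates, 69 per arm and no mITT exclusions. If Part 3 were instead run 1:1:1, 160 mg would not be over-allocated, but it would still have no Part 2 subjects and the exposure would remain.

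**What to change.** 1. **Section 13.4.** Before unblinding, prespecify a Part-stratified 160 mg versus placebo analysis: Cochran-Mantel-Haenszel by Part, or a three-arm logistic model with treatment and Part. At minimum make it a sensitivity analysis, to be read beside the pooled chi-squared result before any development decision on 160 mg. Making it primary is the sponsor's choice.
2. **Section 13.3.** If it is made primary, restate 160 mg power against the stated 85% over a range of N2, using the no-drift figures in step 7.
3. **Sections 8.1 and 11.3.** Reconcile the 1:1:1 wording with the three-part allocation, and state the rule that sets the Part 3 ratio from the realised N2. For 69 per arm, placebo:80 mg:160 mg is (61 − N2/2):(61 − N2/2):61.

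**Cost.** As a sensitivity analysis this is wording only. As a primary analysis it gives up power, steeply for Cochran-Mantel-Haenszel when N2 is large. The logistic model loses less because 80 mg subjects help to estimate the Part effects, but it assumes a constant 80 mg effect on the logit scale. If 80 mg instead adds a constant 17 points, its 160 mg error under Holm with the 5.1% to 10% step is 6.4/7.3/8.0% at N2 = 36/60/80. That is still below the pooled test in step 6, but not at 5%.

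### With few remitters expected, the large-sample chi-squared test lets Holm's second step run to about 6% instead of 5% when one dose works and the other does not

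*Combined protocol and SAP*

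**What the plan says.** Section 13.3 argues for a one-sided framework, "allowing a 5% type I error for the one-sided test of the null hypothesis", and lists "A one-tailed test for proportions" among its assumptions. On multiplicity it refers to "the need of maintaining the experiment-wise error at the nominal alpha level". It also puts the aim more softly: "sample size is increased in order to maintain an overall type I error rate as close as possible to the nominal value of 5" per cent. The increase from 55 to 69 per group is explained by the first Holm step: "the alpha level actually considered is 2.5%, as the Bonferroni-Holm method will require for the significance testing of the lower p-value". Dropouts count as failures, so the placebo rate "equates to a 5.1% Clinical Remission rate" and the high-dose rate "equates to a 22.1% Clinical Remission rate".

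Section 13.4 describes the analysis itself. Each dose is "compared with placebo using the chi-squared test and using the Bonferroni-Holm method to control the false positive error rate". That section does not give the sidedness of the test, whether a continuity correction applies, or whether the p-value is asymptotic or exact. Section 13.1 defers the full detail to a separate SAP, whose text is not among the documents reviewed.

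**The concern.** The chi-squared p-value is a large-sample approximation, and remission on placebo is expected to be rare. In a comparison of placebo with an ineffective dose, both remitter cells have expected counts below 5. In that range the approximate p-value can be too small, particularly at the 5% level that Holm uses for the larger of the two p-values.

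Holm reaches that level only after the other dose has been declared superior. The exposed case is therefore a trial in which one dose works and the other does not, and the error is to declare the ineffective dose effective as well. Section 5.5 calls this a dose-finding study, so a false claim for one dose could affect which dose goes forward.

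**Working it through.** **Inputs.** From 13.3: 69 per group; remission 5.1% on placebo (6% × 0.85) and 22.1% on an effective dose (26% × 0.85); one-sided 2.5% at the first Holm step, hence 5% at the second. From Table 2: placebo rates of 4% to 10%, with the active rate 20 points higher, all multiplied by 0.85. Assumption: the test is the uncorrected Pearson chi-squared, taken one-sided through its signed root.

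**1. The plan's own figures reproduce.** With unpooled variance, n = (z₁₋α + z₀.₈₅)² × [p₀(1−p₀) + p₁(1−p₁)] / (p₁−p₀)².
- Variance sum: 0.051 × 0.949 + 0.221 × 0.779 = 0.2206. Difference: 0.17.
- α = 0.05: (1.645 + 1.036)² × 0.2206 / 0.0289 = 54.9, so 55.
- α = 0.025: (1.960 + 1.036)² × 0.2206 / 0.0289 = 68.5, so 69.
- Power at 69: Φ(0.17 / √(0.2206/69) − 1.960) = Φ(3.007 − 1.960) = 85.2%.

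All seven rows of Table 2 match as well.

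**2. Expected counts.** 69 × 0.051 = 3.5 remitters in placebo and in an ineffective dose arm, so two of the four cells are below 5.

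**3. One table as an example.** Take 5 remitters on the dose and 1 on placebo. The pooled rate is 6/138 = 0.0435, and Z = (4/69) / √(0.0435 × 0.9565 × 2/69) = 1.670. The one-sided p-value is 0.0475, significant at 5%. The exact unconditional p-value for the same statistic, maximised over the common rate, is 0.061.

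**4. Holm false-claim rate.** Sum over the shared placebo count x:

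Σ Pr(x) × [a(x) + (b(x) − a(x)) × c(x)]

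Here a and b are the probabilities that the ineffective dose reaches one-sided 2.5% and 5% given x, and c is the probability that the effective dose reaches 2.5% given x. Exact binomial enumeration at 69 per arm gives:

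| Placebo rate in Table 2 | 4% | 5% | 6% | 7% | 8% | 9% | 10% |
|---|---|---|---|---|---|---|---|
| Uncorrected chi-squared | 6.0% | 6.1% | 6.0% | 5.7% | 5.5% | 5.3% | 5.2% |
| Exact unconditional | 4.8% | 4.6% | 4.6% | 4.6% | 4.6% | 4.6% | 4.5% |

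At the planned rates the chi-squared figure is 5.96%, and a 2,000,000-run simulation gives 5.97%. The source is the second step: the single comparison at nominal one-sided 5% has a true size of 5.99% at a 5.1% rate.

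**5. Both doses ineffective.** The family-wise error is 4.1% at a 5.1% rate and at most 4.6%, within 5%.

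**6. Sensitivity to arm sizes.** At the planned rates, with arms written as placebo / ineffective dose / effective dose, 68/70/69 gives 4.9%, 66/69/69 gives 5.1%, and 69/66/69 gives 5.6%. Equal but smaller arms of 59 to 65, as mITT exclusions might leave, stay near 6.0%. If arm sizes are drawn at random from 62 to 69 (an assumption), the mean is 5.4%. In that exercise 32% of draws are at or below 5%, and some reach 6.2%.

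**7. Power at the first Holm step, 69 per arm, planned rates.** Exact power is 86.2% with the one-sided chi-squared test and 86.0% with the exact p-value. The exact test corresponds to cut-offs of 1.989 and 1.704 in place of 1.960 and 1.645.

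**The case against.** Several points on the other side stand.

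- Section 13.3 describes the decision as whether at least one dose beats control. The excess arises only after a dose that truly works has been declared superior, so a false decision to proceed with a wholly inactive drug is not inflated.
- Section 13.3 asks for an error close to 5% and openly accepts a relaxed false-positive standard because Phase 3 must confirm. One point over 5% in one configuration is arguably near that wording.
- Sections 8.1 and 13.2 lead to approximately, not exactly, equal arms in the primary analysis, and small imbalances shrink or remove the excess.
- The 6% assumes no continuity correction. With one, the one-sided error is at most 3.7%, but exact power falls to 80.2%.
- The separate SAP may settle the version of the test.

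These points limit the size of the problem. They do not remove it, because 13.4 names Holm as the means of controlling the false-positive rate, and Holm's guarantee covers the case of one effective and one ineffective dose only if each p-value is valid.

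A reader might also infer that the trial has 79% power and not 85%. That figure comes from putting the ordinary non-directional chi-squared p-value into Holm at 2.5% and 5%. Exact power then falls from 86.2% to 78.7%, or by the plan's formula from 85.2% to Φ(3.007 − 2.241) = 77.8%. The documents do not support this as the plan's power: 13.3 specifies a one-tailed test throughout, and 13.4 merely leaves the word out.

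**Conclusion.** The point holds as a modest one. If one dose works and the other equals placebo, the test named in 13.4, run one-sided and uncorrected, makes a false claim for the ineffective dose in about 6.0% of trials at the planned rates with 69 per arm. Across Table 2 the range is 5.2% to 6.1%. The equal-arm figure is close to the worst case: slightly unequal arms give about 4.9% to 5.6% at the planned rates.

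It would be wrong to read this as a general failure of error control, since with both doses ineffective the error stays at about 4.1%. The sizing in 13.3 is also reproducible and is not in question. Because a test on the same statistic keeps the error within 5% at almost no cost, the change is worth making before unblinding.

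The conclusion is confined to the primary endpoint. Section 13.6 applies similar methods to the secondary proportions, but no error rates were worked out for them.

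**What to change.** In 13.4 and the separate SAP, for the primary endpoint, replace the chi-squared test with the one-sided unconditional exact test based on the pooled (Pearson) Z statistic. State that Holm applies one-sided 2.5% to the smaller p-value and, if that is significant, one-sided 5% to the other. Writing the sidedness down also prevents a non-directional p-value from being used by default; that part is a clarification of what 13.3 already specifies.

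Effect: at 69 per arm the false-claim rate becomes 4.5% to 4.8% across Table 2, with no change in sample size.

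Cost: two sentences and standard software. First-step power falls by about 0.2 points at the planned rates (86.2% to 86.0%) and about 0.6 at a 4% placebo rate. With slightly unequal arms the loss can be greater, for example about 1.3 points at 68/70/69 and the planned rates. The risk-ratio confidence interval in 13.4 may occasionally disagree with the exact test, so the SAP should say that the test decides significance.

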9.11 Early Termination Visit

The Early Termination Visit is based on the subject's withdrawal from the study prior to Week 8. Participation in the study is completely voluntary. Subjects are also free to withdraw from the study at any time if they feel they are not benefiting from the study in order to receive rescue therapy and/or receive treatment with standard medical care. In addition, the Investigator may discontinue the subject from the study at any time based on his/her assessment of clinical efficacy and/or safety. The decision to discontinue a subject remains the responsibility of the treating physician, which will not be delayed or refused by the sponsor. When a subject withdraws or is discontinued from the study, every effort should be made to complete as many safety and efficacy assessments as reasonably appropriate. Refer to Table 1 for the assessments to be performed at the Early Termination Visit.

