12.1 Prohibited Concomitant Medications and Procedures

The following concomitant medications are prohibited during the treatment portion of the study, Week 0 Visit (Day 1) to the Week 8 Visit, or the Early Termination Visit for subjects who discontinue prematurely during the study:

- Use of any biologic agents, including TNF blockers
- Use of oral aminosalicylates (sulfasalazine [SSZ] or 5-ASA compounds)
- Use of mycophenolic acid, tacrolimus, sirolimus, cyclosporine, or thalidomide
- Use of topical treatment with 5-ASA or corticosteroid enemas or suppositories is prohibited during the study and must be discontinued 2 weeks prior to the Screening Visit
- Use of oral and/or IV corticosteroids is prohibited during the study and must be discontinued 2 weeks prior to the Screening Visit
- Use of AZA, 6-MP, or MTX is prohibited during the study and must be discontinued 8 weeks prior to the Screening Visit
- Chronic use of nonsteroidal anti-inflammatory drugs (NSAIDs).

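### Section 13.4 makes only withdrawal a failure, so a subject who starts prohibited UC therapy and stays on study can be counted as a remitter

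*Combined protocol and SAP*

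**What the plan says.** - **Endpoint (7.1, 13.4).** Clinical remission is defined by the Week 8 MMS and limits on its sub-scores. No condition refers to other therapy taken.
- **Failure rule (13.4).** "Subjects who withdraw will be assumed not to be in remission at Week 8". LOCF fills missing MMS in completers. Nothing is said about scores observed after prohibited therapy.
- **Prohibited therapy (12.1).** "The following concomitant medications are prohibited during the treatment portion of the study", from Day 1 to the Week 8 or Early Termination Visit. The list covers biologics, oral and topical aminosalicylates, corticosteroids, immunosuppressants and chronic NSAIDs. It states neither that a user is withdrawn nor how the Week 8 score is treated.
- **Withdrawal (9.11, 15).** Subjects are "free to withdraw from the study at any time if they feel they are not benefiting", in order to receive rescue or standard care. Section 15 lists protocol violation among the reasons that suffice for stopping the product, the study or both. Neither section makes withdrawal compulsory once prohibited therapy starts, and Section 13.4 does not say whether stopping the product alone counts as withdrawing.
- **Analysis sets (13.2).** The primary mITT set drops only subjects who leave for a documented unrelated reason or who stay under 7 days. The PP set, used for support, drops violations judged likely to affect efficacy.
- **Deferral (13.1).** The comprehensive plan is to be a separate SAP, which is not part of the document reviewed.

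**The concern.** Read together, these sections leave one path open. A subject breaches 12.1 by starting a therapy that can itself induce remission, is not withdrawn, attends Week 8 and meets the criteria. The primary analysis then counts a remission that the assigned treatment may not have produced.

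The path is not far-fetched. Inclusion criterion 7 describes subjects who relapsed on 5-ASA at or below 2.4 g/day, and oral aminosalicylates are then barred, so a familiar treatment is off limits during active disease.

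What is at stake is the contrast between arms. Such remissions on placebo shrink the difference and cost power; on an active arm they are credited to the drug. The trial is sensitive to small numbers: at the planned rates it expects 0.051 × 69 = 3.5 placebo remitters and 0.221 × 69 = 15.2 on the high dose.

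**Working it through.** **Inputs (Section 13.3).** The placebo rate of 6% "equates to a 5.1% Clinical Remission rate" and the high-dose rate of 26% "equates to a 22.1% Clinical Remission rate", both after counting 15% dropout as failure. The plan sets "A power of 85%, type II (β) error = 0.15", and starts from "allowing a 5% type I error for the one-sided test of the null hypothesis". For the final size of 69 per arm, "the alpha level actually considered is 2.5" per cent, because of Bonferroni-Holm.

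**Step 1: reproduce the plan.** With the unpooled normal approximation, n = (z_α + z_β)² × V / d², where

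V = 0.051 × 0.949 + 0.221 × 0.779 = 0.0484 + 0.1722 = 0.2206, and d = 0.17.

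- One-sided 5%: (1.645 + 1.036)² × 0.2206 / 0.0289 = 54.9, so 55.
- One-sided 2.5%: (1.960 + 1.036)² × 0.2206 / 0.0289 = 68.5, so 69.
- Power at 69 per arm: Φ(0.17 / √(0.2206/69) − 1.960) = Φ(1.047) = 85.2%.

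All seven power figures in Table 2 also reproduce, so no stated figure is in dispute.

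**Step 2: add remissions obtained on prohibited therapy.** The documents give no frequency, so this part is assumption. Suppose the subjects concerned would otherwise be non-remitters, and keep the formula, 69 per arm and one-sided 2.5%.

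| Placebo | Active | Difference | Power |
|---|---|---|---|
| 5.1% (plan) | 22.1% | 17.0 points | 85.2% |
| 6.1% | 22.1% | 16.0 points | 79.2% |
| 7.1% | 22.1% | 15.0 points | 72.4% |
| 8.1% | 22.1% | 14.0 points | 64.9% |
| 9.1% | 24.1% | 15.0 points | 67.6% |

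The last row lets active treatment gain 2 points while placebo gains 4. With a pooled variance the first four rows become 83.7%, 77.7%, 70.8% and 63.4%, so the losses are similar.

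**Step 3: how many subjects must take the therapy and stay.** One point is 0.69 of a remitter in 69, but not everyone who takes a therapy remits. Section 5.4 gives 12.1% as the lower active-arm rate in a randomized trial of budesonide-MMX and mesalamine, and 23.37% as the mean for 5-ASA in a review using combined clinical and endoscopic criteria. These definitions differ from the present endpoint, so they serve only as a guide. Number needed = 69 × points / remission rate:

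| Extra placebo points | At 23.37% | At 12.1% |
|---|---|---|
| 1 | 0.69 / 0.2337 = 3.0 | 0.69 / 0.121 = 5.7 |
| 2 | 1.38 / 0.2337 = 5.9 | 1.38 / 0.121 = 11.4 |
| 3 | 2.07 / 0.2337 = 8.9 | 2.07 / 0.121 = 17.1 |

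That is about 3–6, 6–11 and 9–17 of 69 placebo subjects. Therapy begun mid-study has less time to work, and some users might have remitted anyway; both would push the numbers needed up.

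**The case against.** **Rescue mostly goes through withdrawal.** Section 9.11 describes subjects leaving in order to receive rescue, and Section 15 gives lack of effect after 4 weeks and protocol violation as grounds to discontinue. Section 5.5 reports that many Phase 2a subjects left early for no effect or worsening. Such subjects are already failures under 13.4. This stands: a reader might infer that effective rescue on placebo would in general be credited to placebo, and the documents do not support that.

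**Scoring what is observed is a legitimate choice.** A treatment-policy approach uses the Week 8 score whatever else was taken, and the plan states no estimand that this contradicts. It is therefore too strong to say the plan demonstrably misclassifies subjects. But the plan does not declare that approach, and Section 13.3 treats dropouts as failures; a failure rule for prohibited therapy is the natural extension.

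**The direction is not known.** One might expect more such use on placebo, but no figure in the documents shows it. If placebo use dominates, the bias is conservative and does not raise the false-positive rate; if active use dominates, it favours the drug.

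**Other parts of the plan may help.** The PP analysis is a partial check, but it is only supportive, deletes subjects instead of counting them as failures, and leaves the qualifying violations to be settled later. The separate SAP may hold a rule. It cannot be credited unseen, and the only change to the primary method that 13.4 anticipates concerns centre effects.

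**Conclusion.** The gap is real but limited. As written, a subject who starts prohibited UC therapy, is not withdrawn and meets the Week 8 criteria is a remitter in the primary mITT analysis, and no section provides otherwise. It affects only the residual who stay on study.

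The power losses in the table are illustrations. They assume that the extra remissions fall on placebo (or, in the last row, mainly on placebo) and that the subjects would otherwise not have remitted. A reader might take 65% as the expected power; nothing in the documents supports that, since it needs roughly 9–17 of 69 placebo subjects to breach 12.1 and stay. The smallest case, 79%, needs about 3–6.

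This is a worthwhile, inexpensive improvement to the analysis rule. It does not show that the design or sample size is wrong.

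**What to change.** Add to Section 13.4, for every arm: a subject who starts a Section 12.1 medication given for UC (aminosalicylates, corticosteroids, immunosuppressants or biologics, but not NSAIDs) between Day 1 and the Week 8 assessment is a non-remitter, and a non-responder for the secondary responder endpoints, whether or not the subject withdraws. Qualifying use is identified by blinded review before unblinding. Report the analysis of observed Week 8 scores regardless of such use as a sensitivity analysis.

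**Cost.** A short addition to the text. Section 12 already has dose, indication and start and stop dates recorded, so no new data are needed. The sample size stays at 69 per arm, since the rule preserves the planned 5.1% and 22.1%. Observed remission rates may be slightly lower, and an occasional subject with trivial use will count as a failure; the sensitivity analysis shows how much this matters. This is an analysis rule only and changes no clinical management.
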